## 5. Study outcomes

- For the study 1 (validation of deeplex test, Insilixa and Xpert 2nd line):

Drug resistance to INH, RIF, ofloxacin, kanamycin as measured by phenotypic methods and Deeplex method.

Secondary outcome: for both RR- and RS patients programmatic treatment outcome will be recorded.

- For the study 2 (cohort study, on RR patients only):

Three types of unfavorable treatment outcomes will be considered:

- Early treatment failure defined as a culture positive at month 6 of the TB treatment (+/- 2 weeks) not followed by negative consecutive cultures and with molecular confirmation of the similarity of the strain with the baseline one
- End of treatment failure defined as a positive culture at the end of the TB treatment (+/- 2 weeks) not followed by negative consecutive cultures and with molecular confirmation of the similarity of the strain with the baseline one
- Relapse defined as a positive culture after the end of the TB treatment not followed by negative consecutive cultures and with molecular confirmation of the similarity of the relapse strain with the baseline one.

## 6. Data management & Data Collection

### **Data collected:**

For each patient enrolled in study 1 & 2, an expanded laboratory request form will be completed.

For all patients the following data will be collected:

- Baseline characteristics (mostly those collected from routine monitoring, including demographic- and contact information, detailed treatment history including details such as failure vs relapse prior MDR treatment, return after loss to follow-up), risk factors for (resistant) TB
- Phenotypic drug sensitivity tests (phase I of Study 1 only)
- Deeplex results (phase I and II of the Study 1)
- Programmatic treatment outcomes

In addition:

- for the phase 2 of the study 1 (validation of InSilixa and 2nd line Xpert test) the results of these 2 tests (InSilixa and 2nd line Xpert) will also be recorded
- for all patients enrolled as RR, the following additional information will be recorded:
  - monthly FDA results,
  - monthly GeneXpert and culture results,
  - treatment outcomes

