## Synopsis

The proposed DIAMA (DIagnostics for Multidrug resistant tuberculosis in Africa) study aims to address current gaps in the diagnosis and management of patients with Multi-Drug-Resistant (MDR) tuberculosis (TB). Building on existing networks and research collaborations, the project aims to evaluate and implement rapid and accurate molecular tests for resistance to anti-TB drugs, to replace the current dependency on phenotypic drug resistance testing (DST), which takes up to 4 months and is technically so demanding that few laboratories can perform these tests correctly.

The project builds on the World Health Organization (WHO) recommended continuous surveillance of patients for rifampicin resistance. Two African partners with advanced molecular laboratories will establish reference laboratories for the 'Deeplex' assay, a novel multiplex deep sequencing-based drug resistance diagnostic platform that simultaneously provides sequence information of genes that confer resistance to key TB drugs. Partners will recruit all patients with RR TB, and a subset of those with rifampicin sensitive TB. In a first phase, sputum will be shipped for the Deeplex assay, for comparison against phenotypic DST to 1st and 2nd line drugs. In a second phase, InSilixa and Cepheid 2nd line Xpert, two 'lower tech' tests at the last stages of laboratory validations, will be implemented in all countries that have established recruitment of retreatment patients. The InSilixa lab-on-chip assay, powered by a smartphone, is able to query 117 drug resistance conferring mutations at around \$20 per test. The Cepheid Xpert 2nd line cartridge can be implemented in existing Xpert machines used for the Xpert MTB/Rif assays. These two tests will be compared versus the Deeplex assay.

Using the latest advances in e-Health software 'DataToCare', molecular results would be communicated in real time to the National TB Programs, so that MDR patients can swiftly start appropriate treatment.

Lastly, once patients have initiated MDR treatment, they will be monitored for treatment success by faster alternative approaches to the WHO recommended monthly cultures: serial sputum samples will have Fluorescein DiAcetate (FDA) vital stain microscopy and measurement of the bacterial load using the Xpert MTB/Rif.

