## **2. Rationale**

We anticipate that the impact of the DIAMA project, if the results are as promising as expected, will be potentially paradigm-shifting. We foresee that MDR-TB will move from an often terminal illness with grave prognosis to a readily recognizable and treatable disease, in which treatment success can be predicted early, so treatment can be modified in 'real' time. The novel tests that identify specific resistance to particular drugs used for the treatment of resistant TB allow for a way of 'personalized medicine', and by monitoring the impact of specific mutations on the outcome of MDR treatment, we anticipate learning which mutations should lead to treatment modifications in order to enhance the chance of treatment success. In addition, we will learn whether heteroresistance, which is the simultaneous occurrence of bacterial populations with and without resistance, is of clinical relevance. Lastly, the fact that the Deeplex assay gives full sequence information on a large number of genes allows us to detect, for the first time, whether different mutations are common in circulating drug resistant strains in the participating countries in Sub-Saharan Africa. Such results will thus not only inform the treatment algorithms used in clinical trials for MDR-TB, yet also provide fundamental insights into the pathogenesis underlying the development of TB resistance.

Once the validation of the novel diagnostic tests for TB resistance mutations will be completed in the DIAMA proposal, the companies that have developed these tests will

include these results in their respective applications for approval by regulatory authorities, and for endorsement by WHO. The monitoring of MDR patients on treatment with FDA microscopy is readily implementable in most peripheral microscopy centers.

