### 1. Study design:

Two multi center observational studies will be conducted:

- *Study 1:* Cross sectional study for TB cases aged  $\geq 15$  (all RIF resistant (RR) ones (new cases or retreatment patients) and equal number of RIF sensitive retreatment

patients from the same country) with comparison of TB resistance diagnostic test performance at baseline. There are 2 phases in this project; phase 1 is the comparison of Deeplex results against the phenotypic results (Gold standard), phase 2 is the comparison of Insilixa and Xpert 2nd generation results against Deeplex (gold standard).

- *Study 2:* Cohort study of RR-TB patients (recruited in Study 1) under treatment with comparison of the performance of FDA or Xpert compared to solid culture

The study flow chart is placed in annex 1 of this protocol

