## **4. Sample size**

The partners in the proposal expect to recruit at least 80% of the eligible retreatment patients (those with RIF resistance -considered as MDR- and equal numbers of RIF sensitive patients) presenting for diagnosis and care. Based on previous years data, over 4700 patients at risk of RR TB are on average collectively being screened annually out of which 590 (15%) are diagnosed as being RR-TB (Table 2, in Background).

For the validation of the novel tests (Study 1), we will recruit all RR patients and equal numbers of RIF susceptible patients, for a total of 1420 RR- and 1420 RIF susceptible patients. In the table below, we summarize the power we expect to have to detect resistance to the key drugs:

**Table 3.** Sample size considerations against **phenotypic** gold standard (Phase 1), and the **genotypic** gold standard (Phase 2, see study flow chart in Annex 1), with each phase including 1420 patients, half of whom will have RR TB, for a total of 2840 patients.

Drug	Expected prevalence of resistance in RIF R (n=710 each phase)	Expected total prevalence of resistance (n=1420 each phase)	Expected sensitivity and precision against phenotypic test	Expected specificity and precision against phenotypic test	Expected sensitivity and precision against genotypic test	Expected specificity and precision against genotypic test
RIF	710 (100%)	710 (50%)	98% +/- 1%	98% +/-1%	98% +/- 1%	98% +/-1%
INH	675 (95%)	923 (65%)	90% +/- 1%	98% +/-1%	98 +/- 1%	98% +/-1%
FQ	43 (6%)	43 (3%)	85% +/- 8%	98% +/-1%	98%, range 88%-100%	98% +/-1%

RIF= rifampicin, INH=isoniazid, FQ=fluoroquinolones

The estimated prevalence of resistance is based on the WHO report (1) and personal communications. This sample size will be ample to validate these tests for resistance to RIF, isoniazid, and fluoroquinolones, according to established guidelines (9).

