### **Specific tests**

In all settings, smear microscopy with Ziehl-Neelsen (ZN) or auramine/rhodamine (A/R), culture, 1st line drug susceptibility testing (DST) and Xpert MTB/Rif are routinely used. Where 2nd line DST on solid culture is not yet available, the project will help implementing the recommended tests on a routine basis. If implementation is not possible in a reasonable framework, respective samples will be tested in one of the study reference labs (LRM Cotonou, RBC Kigali or ITM Antwerp), together with the Deeplex.

Samples will undergo direct auramine microscopy and direct FDA microscopy. All samples (including AFB negative) will undergo Xpert MTB/Rif testing and culture.

As all partners already conduct phenotypic DST, the culture and first-line phenotypic DST will be conducted on-site, following training for second line DST by the Lowenstein Jensen proportion method as necessary. Participating laboratories will receive periodic External Quality Assessment (EQA) panels from the ITM in Antwerp. Surplus sputum will be stored at

-20C and serves for testing additional bacterial diagnostic tests, such as the InSilixa and Cepheid 2nd line tests available in the second phase of study 1.

Partners are moreover encouraged to follow WHO guidelines regarding the use of Line Probe Assays (LPA) for FQ and injectable resistance for RR patients, which is not part of the DIAMA study protocol. Given the intrinsic delays of shipments in phase I, and the fact that the Deeplex is not yet validated in phase I, the use of such LPAs will support the appropriate choice of treatment regimen for RR patients. The partner laboratories will however be able to request results from Deeplex testing to weigh these 'unvalidated' results in the choice of a salvage regimen in case patients fail their RR treatment.

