## **9. Data Analysis**

For the phase I and II of the study 1 (validation of Deeplex against phenotypic DST & validation of InSilixa and Xpert 2nd generation against Deeplex results), we will validate the molecular assays for their performance (Se and Sp) on the diagnosis of RIF resistance, against phenotypic DST on solid medium as gold standard, with resolution of discordances by classic target sequencing of the *rpoB* gene. Similar analyses will be conducted to determine the performance for the diagnosis of isoniazid and fluoroquinolone resistance.

An interim analysis will be performed after 350 RR-TB patients have been recruited in order to test our assumptions regarding resistance proportions and consider adjustment of sample size or recruitment strategy.

For the study 2, the results will be analyzed with time dependent Cox regression to identify the optimal time point to identify patients who are at risk of failing treatment.

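### The plan contradicts itself on the Phase 2 reference, and if phenotypic DST is recorded in Phase 1 only, InSilixa and Xpert 2nd line can be judged only on agreement with Deeplex

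*Combined protocol and SAP*

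**What the plan says.** Study 1 has two phases: Deeplex against phenotypic DST, then InSilixa and Xpert 2nd line. The plan's statements on the Phase 2 reference point in two directions.

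Towards Deeplex:
- The Synopsis, on InSilixa and Xpert 2nd line: "These two tests will be compared versus the Deeplex assay".
- Methods 1 (Study design) defines phase 2 as InSilixa and Xpert 2nd "generation results against Deeplex (gold standard".
- Table 3 (Methods 4) assigns the genotypic reference to Phase 2.
- Methods 6 (Data collected) keeps Deeplex results in both phases but limits "Phenotypic drug sensitivity tests (phase I of Study 1 only".

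Towards phenotypic DST:
- Methods 9 (Data Analysis) opens with both phases, names InSilixa and Xpert 2nd "generation against Deeplex results), we will validate the molecular assays for their performance (Se and Sp) on the diagnosis of RIF resistance", and continues "against phenotypic DST on solid medium as gold standard, with resolution of discordances by classic target sequencing of the" *rpoB* gene. It promises similar analyses for isoniazid and fluoroquinolones.
- Methods 5 (Study outcomes), under a heading naming all three tests, gives the outcome as resistance measured by phenotypic methods and by Deeplex, with no restriction by phase.

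On availability, Methods 8 (Specific tests) says that in all settings culture and first-line "drug susceptibility testing (DST) and Xpert MTB/Rif are routinely used". Second-line DST, which covers fluoroquinolones, is not yet in place everywhere. The project will help to introduce it or have the samples tested at a reference laboratory.

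**The concern.** The data-collection list decides what can be analysed. If it is followed, no Phase 2 patient has a recorded phenotype, and the analysis that Methods 9 appears to promise cannot be done for InSilixa or Xpert 2nd line. What remains is how often each test gives Deeplex's answer.

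That differs from sensitivity for resistance, because Table 3 (column "Expected sensitivity and precision against phenotypic test") expects Deeplex itself to find only 85% of phenotypic fluoroquinolone resistance and 90% of isoniazid resistance. InSilixa, like Deeplex, works by detecting resistance mutations. A resistant case missed by both is counted as a correct negative, and enrolling more patients does not reveal it. Primary objective 1 is to diagnose resistance to first- and second-line drugs, and the Rationale expects the test developers to "include these results in their respective applications for approval by regulatory authorities" and to seek WHO endorsement. The meaning of the Phase 2 sensitivity figure therefore needs to be settled beforehand.

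**Working it through.** **Inputs (Table 3).** Per phase: 1420 patients, 43 fluoroquinolone-resistant, 923 isoniazid-resistant. Sensitivity against phenotype: fluoroquinolones 85% +/- 8%, isoniazid 90%. Sensitivity against the genotypic reference: 98%. Fluoroquinolone specificity: 98%. No confidence level is stated, so 95% two-sided is assumed.

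**The plan's own figure.** Table 3 gives 98%, range 88%-100%, for fluoroquinolones against the genotypic reference. The exact 95% interval for 42/43 is 87.7% to 99.9%, so this reproduces with n = 43. The phenotypic precision does not: 1.96 x sqrt(0.85 x 0.15 / 43) = 10.7 points, not 8. Counting both phases (n = 86) gives 7.5 points. That might suggest phenotypes were once expected in both phases, but this is only an inference and nothing below rests on it.

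**What Phase 2 leaves unidentified.** Let D be Deeplex sensitivity against phenotype, a the new test's detection rate among phenotypically resistant Deeplex positives, and b its detection rate among phenotypically resistant Deeplex negatives. Then

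sensitivity against phenotype = a x D + b x (1 - D).

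Phase 1 estimates D. Phase 2 estimates agreement among all Deeplex positives; a is assumed equal to it, at 98%. Without a phenotype b is unobserved and can be anything from 0 to 1.

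| Drug | D | Lower end (b = 0) | Upper end (b = 1) |
|---|---|---|---|
| Fluoroquinolones | 85% | 0.98 x 0.85 = 83.3% | 83.3% + 15% = 98.3% |
| Isoniazid | 90% | 0.98 x 0.90 = 88.2% | 88.2% + 10% = 98.2% |

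At either end, sensitivity against Deeplex is the same 98%. Over Table 3's own margin for D, the fluoroquinolone range is 75.5% to 98.5% at D = 77% and 91.1% to 98.1% at D = 93%.

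**Dropping the assumption on a.** With 43 resistant and 1420 - 43 = 1377 susceptible patients, Deeplex has 43 x 0.85 = 36.6 true positives, 6.5 missed cases and 1377 x 0.02 = 27.5 false positives. That makes 64 positives, of which 36.6/64 = 57% are phenotypically resistant. Sensitivity of 98% against Deeplex allows 0.02 x 64 = 1.3 misses; if all fall on resistant patients, the lower end is (36.55 - 1.28)/43 = 82.0%. Specificity of 98% against Deeplex allows 0.02 x (1420 - 64) = 27 extra positives, enough to include all 6.5 missed cases, so the upper end is 100%. The range widens slightly, to 82% to 100%.

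**What recording phenotypes would give.** If all 43 had a result, 36/43 has an exact 95% interval of 69.3% to 93.2%. An exact one-sided 0.025 test of 98% (reject at 39/43 or fewer; actual level 0.011) has 94% power when the truth is 83.3%. With an assumed 10% to 30% of results missing (n = 39 to 30), power is about 84% to 91%. For isoniazid, 88.2% on 923 patients has a half-width of 1.96 x sqrt(0.882 x 0.118 / 923) = 2.1 points.

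**The case against.** Staged validation is a deliberate choice: the complex assay against phenotype first, then simpler tests against the complex assay. The Synopsis gives a reason, since phenotypic testing is slow and few laboratories do it well. Table 3 labels its columns by reference, so a careful reader will not confuse the two sensitivities. This stands, and it is why Deeplex should remain the Phase 2 reference.

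Several stronger readings are tempting but not supported:

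- *That Phase 2 scores the new tests only against Deeplex.* Methods 5 and 9 appear to carry a phenotypic standard into Phase 2. What is documented is a contradiction.
- *That the plan discards fluoroquinolone DST which every site already runs.* Routine testing in all settings is documented for first-line drugs only. The Deeplex technical background also foresees inactivating referred sputum once phenotypic assays are no longer needed, and an inactivated sample cannot be cultured.
- *That Phase 2 cannot tell an 83% test from a 98% test.* These are the extreme ends for a test agreeing 98% with Deeplex. A test that reached 83% by missing Deeplex-positive cases would be exposed.
- *That both ends are equally likely.* If the new tests read the same gene targets as Deeplex, the lower end is more plausible. The planned Phase 1 and Phase 2 results already give that end as a product, but they do not show where in the range a test lies.
- *That a 98% sensitivity will go to regulators.* The 98% is a planning assumption, and the Rationale refers to the validation results without giving a figure.

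**Conclusion.** The point holds as an internal conflict with a measurable consequence. Methods 6 as written prevents the phenotypic analysis that Methods 9 appears to specify for InSilixa and Xpert 2nd line. Phase 2 would then support statements about agreement with Deeplex, leaving sensitivity against phenotypic DST undetermined between about 83% and 98% for fluoroquinolones and 88% and 98% for isoniazid. The isoniazid range applies only to a test that reports isoniazid; the plan describes the Xpert 2nd-line cartridge for second-line drugs only.

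The ranges rest on Table 3's planning values, on 98% agreement holding among phenotypically resistant Deeplex positives, and on phenotypic DST as the yardstick, which is itself imperfect. They are bounds, not a prediction of poor performance. The plan should be corrected on this point; the staged design need not be abandoned.

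**What to change.** 1. **Methods 6, Data collected:** record phenotypic DST results in phases 1 and 2 wherever they are produced, first-line in all settings and second-line where available.
2. **Methods 9:** state that Deeplex is the Phase 2 reference. Add that sensitivity and specificity of InSilixa and Xpert 2nd line against phenotypic DST are also reported among patients who have a result, with the number available for each drug.
3. **Reporting:** describe the Deeplex comparison as agreement with Deeplex, not as sensitivity for resistance.
4. **Methods 1 and 5:** align them with this wording, so that all sections name the same Phase 2 reference and outcomes.

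The cost is one data-collection line, a clarified analysis paragraph and one extra table. First-line results need no new test. For fluoroquinolones, the results that matter for Xpert 2nd line, this captures only what sites or reference laboratories produce; full coverage might need extra testing. The estimate may therefore be incomplete, and patients with a result may differ from those without. Even complete data would be imprecise, at 69% to 93% for 36/43.

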**Database:**

A Master database will be developed by Savics company together with the central study Data Manager (DM) of Benin. A unified data entry system will be used, with a unique identifying number for each patient who is recruited in the study.

**Data entry and control:**

Each partner will be responsible for regular data entry with built-in validation checks, internal quality control and regular back-up. All data collected will be kept in a secure place with access restricted to study staff.

The Study Data Manager of Benin will remotely follow data entry. Quality control checks will be performed. After review of the files, necessary queries, if arising, will be immediately addressed to the country-site data manager for clarification using patient query forms. After resolution of the queries, corrected data will be entered in the database. All databases will be secured with password-protected access systems.

## **7. Patient management**

An informed consent form will be required to be signed by all patients enrolled in the studies.

For minors, an assent will be sought for participating in the studies and a legal representative will provide consent.

If patients or legal representative are illiterate a literate witness will check that the consent process is done as per scheduled and will sign the consent form.

Patients found to have RR-TB will be referred to initiate MDR-TB treatment and will be eligible to participate in both Study 1 and Study 2, while the RIF sensitive patients will participate in Study 1 only.

RR TB patients will be followed during the whole course of the MDR-TB treatment, as per routine recommendations (study flow-chart in annex 1).

## 8. **Laboratory procedures**

### **Sampling schedule**

The DIAMA project is based on routine diagnosis and patient management.

While country TB programs recommend collecting sputum samples, a maximum of two additional samples will be asked at the same visit.

All patient interventions and associate laboratory tests are summarized in Table 4 below.

**Table 4.** Schedule of assessment

	Screening 	Enrollment 	Follow up 
Medical/demographic history	X		
Informed Consent		X	
Sputum collection	X	X	X
Programmatic outcome follow-up 			X

 Includes routine programmatic interventions

 May be combined with screening

 RR patients only

As no additional visit is required, and intervention is minimal, no compensation fee will be given to the participants.

### **Specific tests**

In all settings, smear microscopy with Ziehl-Neelsen (ZN) or auramine/rhodamine (A/R), culture, 1st line drug susceptibility testing (DST) and Xpert MTB/Rif are routinely used. Where 2nd line DST on solid culture is not yet available, the project will help implementing the recommended tests on a routine basis. If implementation is not possible in a reasonable framework, respective samples will be tested in one of the study reference labs (LRM Cotonou, RBC Kigali or ITM Antwerp), together with the Deeplex.

Samples will undergo direct auramine microscopy and direct FDA microscopy. All samples (including AFB negative) will undergo Xpert MTB/Rif testing and culture.

As all partners already conduct phenotypic DST, the culture and first-line phenotypic DST will be conducted on-site, following training for second line DST by the Lowenstein Jensen proportion method as necessary. Participating laboratories will receive periodic External Quality Assessment (EQA) panels from the ITM in Antwerp. Surplus sputum will be stored at

-20C and serves for testing additional bacterial diagnostic tests, such as the InSilixa and Cepheid 2nd line tests available in the second phase of study 1.

Partners are moreover encouraged to follow WHO guidelines regarding the use of Line Probe Assays (LPA) for FQ and injectable resistance for RR patients, which is not part of the DIAMA study protocol. Given the intrinsic delays of shipments in phase I, and the fact that the Deeplex is not yet validated in phase I, the use of such LPAs will support the appropriate choice of treatment regimen for RR patients. The partner laboratories will however be able to request results from Deeplex testing to weigh these 'unvalidated' results in the choice of a salvage regimen in case patients fail their RR treatment.

